6.2 Unscheduled Visits

Unscheduled visits may be conducted at any time for safety reasons, if deemed medically necessary by the investigator. During such visits vital signs, height, weight, VAS, ODI, concomitant treatments, neurological exam and AE evaluation will be required, while all other assessments may be performed at the investigator's discretion.

For any subjects who are planning an intervention during the course of the study, every effort should be made to schedule an "unscheduled visit" within a 30-day time window prior to the intervention. Surgical and injection interventions should be avoided through at least the 24 month primary endpoint follow-up. Surgical and injection interventions should only be undertaken if the subject's pain, measured by VAS, and function, measured by ODI, are not improved compared to the baseline values since an intervention could confound the efficacy assessments and would classify a subject as a treatment failure. During this visit, vital signs, height, weight, VAS, ODI, concomitant treatments, neurological exam and AE evaluation will be required, while all other assessments may be performed at the investigator's discretion. However, if the subject's originally scheduled visit falls within 30 days prior to the planned intervention, the unscheduled visit will not be necessary. Such visits will allow for subject-reported efficacy assessments (VAS and ODI) to be used in last observation carried forward (LOCF) analysis. Details of this analysis are provided in Section 9.9.

6.3 Missing or Delayed Study Visits

Subjects should be encouraged not to miss any visits. Any visits that are missed or not completed within the specified timeframe (or window allowance) should be documented by the site and the CRA should be notified.

If a scheduled in-clinic visit is missed, the site should contact the subject to determine if any interventions that would classify the subject as a treatment failure have occurred since their last visit. If any interventions are reported, the site should collect all the information required if the intervention had been reported at an in-clinic visit. All intervention information collected remotely must be documented in a source document and/or worksheet.

6.4 Screening Assessments

6.4.1 Subject Demographics/Other Baseline Characteristics

Demographic and baseline characteristics will be recorded during the screening period. This includes the following: demographics, including past and current smoking history, medical and surgical history including, but not limited to, surgical history of the spine (including all invasive spinal interventions) and history of packed red blood cells and platelets administration, vaccinations and pregnancies (where applicable).

Subjects will also be asked to provide medical records or access to medical information relating to any healthcare utilization that has occurred up to 12 months prior to treatment. However, this is optional and will not impact a subject's participation in the study.

6.4.2 Pre-Treatment Pain Medication Usage Collection by E-Diary

Baseline pain medication usage must be established prior to diagnostic injection procedures if performed during the screening. A minimum of 10 out of the 14 daily entries must be complete in order to establish a baseline dose. If more than 4 out of 14 daily entries are missing, subjects should be asked to continue completing the e-diary until 10 out of 14 daily entries are obtained.

Based on the opioid information entered into the e-diary during baseline, subjects will be classified into one of the following groups:

- **Opioid Non-user:** subjects who did not take any opioids during the e-diary pain medication data collection period
- **Opioid user:** subjects who did take an opioid during the e-diary pain medication data collection period.

6.4.3 Prohibited Concomitant Medication and Procedures

Subjects should be encouraged not to receive any of the following medications or treatments during the course of the study and/or for the times specified below:

- Chronic (at least 7 consecutive days) systemic corticosteroids at a dose equivalent to
 ≥ 10 mg/day of prednisone are prohibited from 14 days prior to the study treatment
 injection. Topical, nasal, and inhaled corticosteroids are permitted. Use of systemic
 corticosteroids post-treatment are not prohibited, but should be discouraged so that an
 accurate assessment of the treatment's effectiveness can be made.
- Systemic NSAIDS and local injections of NSAIDs into the treated disc and and/or adjacent vertebral discs are prohibited from 7 days prior to the study treatment injection. Use of NSAIDS post-treatment are not prohibited, but should be discouraged so that an accurate assessment of the treatment's effectiveness can be made.

- Any lumbar intradiscal injection procedure (e.g., injection methylene blue, dextrose, PRP, or glucosamine and chondroitin sulphate) at the treated disc other than discography or epidural steroid injection prior to treatment injection are prohibited. The injection of contrast medium must be done at least 2 weeks prior to study treatment procedure.
- Use of surgical procedures or intradiscal injections should be avoided through at least the 24 month primary endpoint so that an accurate assessment of the treatment's effectiveness can be made. Surgical and injection interventions should only be undertaken if the subject's pain, measured by VAS, and function, measured by ODI, is not improved compared to the baseline values since an intervention could confound the efficacy assessments and would classify the subject as a treatment failure.
- Epidural steroid injections within 8 weeks prior to study treatment. Use of epidural steroids post-treatment are not prohibited, but should be discouraged so that an accurate assessment of the treatment's effectiveness can be made.
- Other investigational therapy or device within 6 months prior to the treatment injection and/or plans to participate in any other allogeneic stem cell/progenitor cell therapy trial for the 36-months following.

6.4.4 Concomitant Treatments

Subjects may continue with all other baseline medication(s). If for any reason, a subject requires additional medication(s) or a change in the dose of existing medication(s), the medication(s), route of administration, and the reason for which it was given should be recorded. During the course of the study, a subject may decide to use over the counter medication(s). As with prescription medications, all over the counter medication(s), including herbal medications must be recorded.

Furthermore, subjects will be asked about medications and treatments to deal with their low back pain at each follow-up visit in addition to asking about potential AEs and other medications being taken.

6.4.5 Determination of Baseline Bone Mineral Density

Prior to treatment, each female subject will be screened for risk of osteoporosis using the Simple Calculated Osteoporosis Risk Estimation (SCORE) and each male subject will be screened for risk of osteoporosis using the Male Osteoporosis Risk Estimation Score (MORES). Any female subject with a SCORE of ≥ 6 or a male subject with a MORES score of ≥ 6 will require a lumbar spine DEXA scan to be performed or, alternatively, a historic T-score to be obtained, if the prior

scan was taken within 6 months prior to the estimated date of study treatment. Similarly, subjects who are considered at risk, as defined in exclusion criterion #4 (Section 6.4.5), will be required to have a DEXA scan at screening, regardless of SCORE value.

The DEXA scan will measure bone mineral density and determine whether or not the subject is considered to have osteopenia or osteoporosis. A T-score that is within \leq -2.5 standard deviations from the standard will exclude a potential subject from participating in this study.

6.4.6 Determination of Baseline SI Joint Pain

A targeted physical examination to rule out SI joint pain will be performed at screening. Clinical examination of the subject's lumbar spine and pelvis should be performed. As part of this examination, the following Laslett's Tests⁵⁹ should be performed.

Test	Description (Positive Findings)					
Distraction	Patient supine. Examiner applies posterolateral directed					
Distraction	pressure to bilateral ASIS. (Reproduction of pain)					
	Patient side-lying. Examiner compresses pelvis with					
Compression	pressure applied over the iliac crest directed at the					
	opposite iliac crest. (Reproduction of symptoms)					
Thigh Thrust	Patient supine. Examiner place hip in 90 deg flexion and					
	adduction. Examiner then applies posteriorly directed					
	force through the femur at varying angles of					
	abduction/adduction. (Reproduction of buttock pain)					
Sacral Thrust	Patient prone. Examiner delivers an anteriorly directed					
Sacial Illust	thrust over the sacrum. (Reproduction of pain)					
Gaenslen's	Patient supine with both legs extended. The test leg is					
	passively brought into full knee flexion, while the					
	opposite hip remains in extension. Overpressure is then					
	applied to the flexed extremity. (Reproduction of pain)					

Table 4: Physical Examination for Evaluation of SI Joint Pain

Subjects who present with all of the following symptoms should be considered positive for SI joint pain:

- 1. Maximal tenderness at or below L5,
- 2. Tenderness over the posterior superior iliac spine / sacral sulcus, and
- 3. Three positive SI joint provocation tests (Laslett's tests).

Should the results of the targeted examination prove inconclusive, the investigator may perform a diagnostic injection of anesthetic to the SI joint in order to determine presence of SI join pain.

6.4.7 **Pregnancy Tests**

A serum pregnancy test will be analyzed for all females of childbearing potential at screening. Women of childbearing potential are defined as premenopausal and not surgically sterilized or postmenopausal for fewer than 2 years. A urine pregnancy test will be performed prior to administration of study treatment to confirm a negative result. If the urine pregnancy test is positive, study drug will not be administered that day, and the result will be confirmed by a serum pregnancy test.

Serum pregnancy tests will be performed at the central clinical laboratory, whereas urine pregnancy tests will be performed by qualified clinical site personnel using kits.

There must be at least a 2-week "washout" period following the diagnostic disc injection and prior to the injection of study treatment (i.e., any injection of contrast media into the disc must be performed at least 2 weeks prior to the study treatment injection procedure).

If an injection of contrast media was performed within 6 months prior to the rexlemestrocel-L injection procedure and presence/absence of full thickness annular tears is documented, it will not have to be repeated.

6.4.9 Worksheets for DSM-5 Criteria for Alcohol and Substance Abuse Disorder

Subjects will complete the Worksheets for DSM-5 Criteria for Alcohol and Substance Abuse Disorder to determine whether they may have an alcohol or substance abuse problem that could inhibit their participation in the study or accurate assessment of the effect of treatment on their low back pain. Any subject answering yes to 6 or more questions on either worksheet are excluded from the study.

6.4.10 Mental Illness/Incompetence

Subjects will complete certain portions of the DSM-5 Self Rated Level 1 Cross-Cutting Symptom Measure-Adult to determine if the subject has mental illness or incompetence that would preclude participation. Subjects will complete Domain1-Depression, Domain 6-Suicidal Ideation, Domain 7-Psychosis and Domain 9-Memory. Subjects with a response of "Severe/Nearly Every Day" (Score of 4) to any question in Domains 1, 6 and 9 are excluded from the study. Subjects with a response of "Slight Rare, Less Than a Day or Two" or greater (Score of 1-4) to any question in Domain 7 are excluded from the study.

6.4.11 Pain Catastrophizer Scale

Subjects will complete the Pain Catastrophizer Scale to determine whether they are a pain catastrophizer. Pain catastrophizers are less likely to receive benefit from any treatment for pain and should be excluded from the study. Subjects that have a score of 30 or more on the pain catastrophizing scale are excluded from the study.

6.4.12 Discography, if performed

Physicians may use a discography procedure to assist in determining what level should be treated

Discography is not required to be performed on all subjects.	

NOTE: The diagnostic injection to determine if the annulus is intact can be performed as part of the discography procedure as long as all of the information required to be collected during the diagnostic injection is collected during the discography procedure.

6.5 Administration of Investigational Product

All subjects in this study will undergo an intervertebral lumbar injection into the target disc with 1 of 3 possible treatments:

• "rexlemestrocel-L alone":

2.0 mL of rexlemestrocel-L cells in freeze media (containing approximately 6 million rexlemestrocel-L cells) mixed in a 1:1 ratio with saline

"rexlemestrocel-L + HA": 2.0 mL of rexlemestrocel-L cells in freeze media solution (containing approximately 6 million rexlemestrocel-L cells) mixed in a 1:1 ratio with 1% HA

• saline control: 2.0mL saline solution.

Vital signs will be recorded prior to injection.

The treatment injection should be performed with a pressure manometer syringe provided by the sponsor.

The injection procedure MUST be stopped if any of the following occur:

- The investigator cannot accurately place the needle tip in the nucleus pulposus
- The injection pressure is greater than 100 psi
- The subject becomes hemodynamically unstable during the injection procedure.

The following information regarding the treatment procedure must be documented in source documentation:

- Procedure start and stop time, including start time of thaw
- Treatment administration stop time
- Treatment interruption information, if applicable
- Opening pressure of the treated disc
- Pressure when 2mL of treatment is injected
- Maximum injection pressure achieved
- Total volume of treatment injected
- Anesthesia type(s).

The following evaluations will be performed after procedure, but prior to discharge:

- Record vital signs
- Perform a disease targeted/abbreviated physical examination
- Perform a neurological examination (motor, sensory, reflex) to assess if the injection procedure has resulted in any neurologic changes. This will be performed by the unblinded health care professional performing the injection procedure, to avoid the potential unblinding of the blinded evaluator. The neurologic exam should be performed after the treatment injection but prior to discharge.
- Prescribe post-injection rehabilitation/treatment and record any prescriptions for postprocedure pain
- Record concomitant medications
- Record adverse events.

All injection and post-procedure care (anesthesia, prophylactic antibiotics, rehabilitation regimens, etc.) will be performed in accordance with standard of care.

Subjects will be given the following directions for post-injection rehabilitation/treatment:

- Day of Procedure Bed Rest
- Day After Procedure Gentle Ambulation with gradual increase thereafter
- Days 1 to 3 Avoid repetitive bending, stooping and lifting greater than 10-15 lbs.
- Return to normal daily activity when pain has subsided to their baseline.

Discharge instructions will include, as needed, prescriptions for pain management. Subjects should be encouraged to remain on the medication they were taking prior to treatment for the first 24 months following treatment. Following study treatment, each subject should adhere to the prescribed post-injection rehabilitation/treatment. Additional guidance can be found in the IP Manual.

The injection procedure is deemed to be completed upon discharge of the subject. After discharge of the subject, the unblinded health care professional should have no involvement in assessing the subject for the protocol or making treatment decisions for the subject.

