4.3 Information to be collected for Screen Failures and Randomized Not-treated Subjects

Subjects who fail any inclusion/exclusion criteria up to the timepoint of randomization are considered screen failures. Subjects who are randomized but do not receive treatment are considered randomized not-treated subjects.

The following information must be recorded for all screen failures and randomized not-treated subjects: demography, medical history, concomitant treatment, inclusion/exclusion criteria met and not met, adverse events, if any, and reason for screen failure or withdrawal. If diagnostic injection for confirmation of full thickness annual tears was performed, information regarding the procedure will also be collected.

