4.5 Subject Withdrawal

Subjects will be free to withdraw from the study at any time, for any reason.

A subject also may be withdrawn/removed by the investigator, if necessary, to protect the subject's health. The investigator has the right to withdraw subjects from the study in the event of intercurrent illness, adverse events, administrative, or other reasons. Any reasons for withdrawal must be documented and explained to the subject.

It is understood, however, by all concerned, that an excessive rate of withdrawals can render the study uninterpretable. Therefore, unnecessary withdrawal of subjects should be avoided.

If for any reason a treated subject is withdrawn from study participation, the reason for and date of withdrawal from the study must be recorded. If the reason for withdrawal is an adverse event or a clinically significant abnormal laboratory test result, monitoring will continue until the event has resolved, stabilized, or until the follow-up period is complete.

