9.3.3 Full Analysis Set (FAS)

The FAS analysis set includes all subjects who are randomized and treated or randomized with an attempt to administer treatment (i.e. subjects taken to procedure room to receive treatment whether administered or not). In these analyses, subjects will be analyzed according to the treatment to which they were randomized (not actual treatment received). Subjects that were randomized but dropped out prior to attempting treatment will be omitted from the FAS analysis set.

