9.3.6 Safety Analysis Set

The safety analysis set will contain all subjects who were randomized and received treatment, and subjects will be classified according to the actual treatment received. Safety analysis set will be used for the safety analyses.

If there is any doubt whether a subject was treated or not, they will be assumed treated (randomized treatment) for the purposes of analysis.

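### A subject whose injection procedure is started but delivers no product falls outside the Safety Analysis Set, so procedural harms in that subject are missing from the safety summaries

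*Combined protocol and SAP*

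**What the plan says.** Section 6.5 sets a mandatory stop: "The injection procedure MUST be stopped if any of the following occur". Three triggers are given. One is about placement, where "The investigator cannot accurately place the needle tip in the nucleus pulposus". Another is a pressure limit, met when "The injection pressure is greater than 100 psi". The remaining one is about the subject's condition, namely that "The subject becomes hemodynamically unstable during the injection procedure". The same section has the total injected volume and the type of anaesthesia documented. It also requires vital signs, a physical and a neurological examination and adverse event recording before discharge.

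Section 9.3.6, repeated in the synopsis, reads: "The safety analysis set will contain all subjects who were randomized and received treatment". Subjects are grouped by what they actually received. A tie-break treats a subject as treated, in the assigned arm, when it is uncertain whether treatment took place. Section 9.7 names this set for the safety endpoints, and 9.7.1 includes the severity of adverse events and their relationship to procedure and treatment.

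The Full Analysis Set in 9.3.3 goes further. It counts attempted administration, explained as "subjects taken to procedure room to receive treatment whether administered or not".

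On status, 4.3 says: "Subjects who are randomized but do not receive treatment are considered randomized not-treated subjects". It gives a short list of data for them, which includes adverse events and names no later visits. Section 5.6 uses the same label for subjects found ineligible on re-examination just before the injection, or who withdraw consent before treatment. The synopsis follow-up statement covers all subjects for 36 months, counted from treatment.

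**The concern.** The intradiscal procedure carries its own risks, which Section 1.7.8 sets out: damage from the needle to nearby structures, discitis and nerve injury. A table of procedure-related events should therefore count everyone who underwent the procedure. As written, membership of the set depends on whether product was delivered, and that is decided during the procedure itself. One of the three stop reasons, haemodynamic instability, is also a harm. If it occurs before delivery, the event that belongs in the table is what removes the subject from it. The exclusion takes place after randomisation and is related to outcome, so the likely direction of error is to understate procedural risk.

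**Working it through.** The plan states no figure for this, so there is nothing to reproduce. The main check is a comparison of definitions. The arithmetic only shows scale under stated assumptions.

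**1. Which stops give zero volume.** Failed placement naturally precedes delivery. Instability may come before or after it. Pressure above 100 psi is normally read while injecting, so some product may already be in. Zero volume is therefore a foreseeable result of the first trigger and a possible result of the third. The second more often gives a partial volume.

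**2. Where a subject with a started procedure and a recorded 0 mL falls.**

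| Section | Condition | Result |
|---|---|---|
| 9.3.2 ITT | randomised | in |
| 9.3.3 FAS | randomised, and treated or attempted | in |
| 9.3.4 As Treated | randomised, grouped by product given | in, but no group is defined for 0 mL |
| 9.3.6 Safety | randomised and treatment received | out |
| 4.3 status | randomised, no treatment received | randomised not-treated |

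The tie-break in 9.3.6 does not help here. It needs doubt about treatment, and 6.5 has the volume written down, so a recorded zero leaves none. A partial volume is less clear: the plan does not say whether it counts as treatment received, and the tie-break may cover it.

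**3. How many subjects.** N = 360, about 120 per arm (Section 3.1). The zero-volume stop rate s is not given; I assume 0.5% to 5%. Expected number = 360 × s; chance of at least one = 1 − (1 − s)^360.

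| s | Expected of 360 | Per arm | Chance of at least one |
|---|---|---|---|
| 0.5% | 1.8 | 0.6 | 0.835 |
| 1% | 3.6 | 1.2 | 0.973 |
| 2% | 7.2 | 2.4 | 0.999 |
| 5% | 18 | 6 | 1.000 |

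**4. How many harms.** Let h be the share of zero-volume stops caused by instability, assumed 10% to 100%. Stop-triggering harms outside the set = 360 × s × h. This runs from 360 × 0.005 × 0.1 = 0.18 to 360 × 0.05 × 1 = 18. For other needle complications, Section 1.7.8 gives less than 1% for discography. Even at s = 5%, that is fewer than 18 × 0.01 = 0.18 expected events.

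**5. Effect on a reported rate.** For illustration, take 3.6 procedural events (1% of 360) among subjects who received product, and h = 1/3.

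- s = 1%: all attempted (3.6 + 1.2)/360 = 1.33%; Safety Analysis Set 3.6/356.4 = 1.01%.
- s = 2%: (3.6 + 2.4)/360 = 1.67%; 3.6/352.8 = 1.02%.
- s = 5%: (3.6 + 6)/360 = 2.67%; 3.6/342 = 1.05%.

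The difference comes from the numerator. The change in denominator is negligible.

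**The case against.** The strongest reply is that nothing is hidden. Section 6.5 requires same-day examinations and event recording. Section 7.1.1 captures adverse events from consent and includes harms of protocol-mandated interventions. Section 8.1 requires every serious event after consent to be reported, and 4.6 intends all adverse events to be followed to resolution, stabilisation or the end of follow-up. The unblinded DSMB is notified of serious events (12.1), and the TEC adjudicates relationship to the procedure (12.2). All of this stands, and it confines the problem to the analysis set. Collecting an event does not put it in the table, however, and 9.7 names no other set.

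A safety set of treated subjects is conventional, and unexposed subjects dilute product event rates. That is a fair reason to show them separately. It does not justify leaving them out of the procedure-related summaries.

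Screening makes placement failure less likely: exclusion 26 removes subjects whose nucleus cannot be injected, and a contrast injection of the disc comes first. This supports a small number, not zero.

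A reader might infer that these subjects also lose scheduled follow-up, because 4.3 lists no visits and a 4.5 provision on withdrawal opens with "If for any reason a treated subject is withdrawn from study participation". The documents do not support that. No sentence ends their visits, 4.6 is not limited to treated subjects, the synopsis follows all subjects, and 5.6 suggests that the label was meant for people who never reach the needle. Because visits are counted from Day 0 and described as post-treatment, the schedule for these subjects is unclear, but it is not withdrawn.

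Finally, the public file contains no separate SAP text and parts of Section 9 are redacted, so a fuller definition elsewhere cannot be ruled out.

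**Conclusion.** The point holds as a gap in the definition of the Safety Analysis Set. Followed literally, 9.3.6 excludes a documented zero-volume subject from the only set used for safety endpoints, while 9.3.3 includes that subject in an efficacy sensitivity set. Procedural risk could be understated. The size is unknown and probably small: about 2 to 18 of 360 subjects under the assumed 0.5% to 5% stop rate, with only a share of those stops being harms in themselves.

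Two stronger readings are not supported. A reader might infer that the loss differs by arm because the three mixtures differ, but a mixture that never entered the disc cannot have caused a failed placement or an instability before delivery. A reader might also infer that instability would appear in the tables as zero. It would not: instability after any product has entered can still be counted, and only the pre-delivery cases drop out.

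**What to change.** In 9.3.6 and the synopsis, define the Safety Analysis Set as all randomised subjects in whom the injection procedure was started. Group them by the product actually delivered or, if none was, by assigned arm. Show subjects with no product delivered on a separate line, and state how partial volumes are classified.

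Reconcile 4.3 with 5.6 and with the synopsis follow-up statement, so that it is clear which status and which visit schedule apply to a subject whose procedure was started but delivered no product. Which schedule that should be is for the sponsor to settle. The stop criteria in 6.5 are not in question.

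The cost is wording in a few places. A few subjects without product exposure enter the denominators; the separate line keeps product-related rates readable.
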